12.3 Analysis Populations

12.3.1 Intent-to-Treat Population

The intent-to-treat population will consist of all subjects, who are randomized and receive study treatment (GS010 or sham treatment). This population will be the population for the primary efficacy analysis.

12.3.2 Safety Population

The safety population is defined as those subjects who received IMP. This population will be used as the population for all safety analyses.

12.4 Statistical Methods

12.4.1 Primary Analysis and Associated Planned Analyses

The primary analysis will be performed on the ITT subject population, which consists of all randomized and treated subjects. The change from baseline to Week 48 in the LogMAR acuity will be the primary response. The ETDRS score will not be directly used because there is a clear relationship between the mean and variance and according to Taylor's power law ($\log SD^2 = 1.743 \log \text{mean} + 0.48$, $R^2 = 0.839$) the best transformation is the logarithm (slope close to 2 and ease of interpretation of the difference in means of log). Because LogMAR is a logarithmic scale and is well known by ophthalmologists, this scale is retained as the primary one. The change from baseline of the treated eye will be compared to the change from baseline of the sham eye using a mixed model including the subject, the treatment and the baseline as covariates.

The center will not be included in the analysis as the number of subjects recruited per site will be very small. The difference in the mean change from baseline to Week 48 between the two treatment groups and associated 95% confidence interval will be reported. Alternative non parametric analysis (signed Wilcoxon test) will be performed as a sensitivity analysis to decrease the influence of possible outliers.

The treatment effect reflects well the effect on the better- and worse-seeing eye if no marked interaction between the eye status (better- versus worse-seeing) and treatment exists. To verify this hypothesis, a model including the subject as a random factor, the treatment as a fixed factor as well as the eye status (better- or worse-seeing) and the interaction between eye status and treatment will be fitted. If the P-value of the interaction test is below 0.15 a potential interaction is detected. In that case the better-seeing eye treated with GS010 will be compared to the better-seeing eye treated with sham and the worse-seeing eye treated with GS010 will be compared the worse-seeing eye treated with sham in an ANCOVA model including the LogMAR at baseline and the treatment. The study is then powered ($1-\beta = 0.8$) to detect a difference of approximately 30 letters between the two treatments.

A meta-analysis combining study GS-LHON-CLIN-03A (RESCUE) and study GS-LHON-CLIN-03B (REVERSE) is planned to verify whether the treatment effect at Week 48 as well as at Week 96 is dependent upon the time from onset of disease. If the treatment effect does not depend upon the eye status, a model using the change from baseline as the response, the subject as a random factor, the treatment as a fixed factor, the time from the onset of disease as a covariate and the interaction between the treatment and the time from the onset will be fitted. If the treatment effect is not the same in the better-and worse-seeing eye, a model will be fitted for the better-seeing eye and another model will be fitted for the worse-seeing eye. The subject factor will not be included in the model, but the LogMAR at baseline, the treatment, and the time from onset of disease will be included.

The generalizability of the treatment effect across countries will be addressed in the meta-analysis because the number of subjects per country could be sufficient to detect major heterogeneity.

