#### Secondary analysis of primary variable for EMA

Secondary Analysis of primary variable for EMA will be based on the methodology for primary analysis of primary variable for FDA stated below using ANCOVA. For secondary analysis change of LogMAR from baseline at Week 48 will be compared between best-seeing GS010 eyes and best-seeing Sham eyes (inter-subject comparison). Also for secondary analysis change of LogMAR from baseline in worst-seeing eyes treated with GS010 will be compared worst-seeing eyes treated with Sham.

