### Primary Analysis for FDA

The null and alternative hypotheses for the primary endpoint are defined below

$$H_0: \mu_{\text{best-GS010}} = \mu_{\text{best-Sham}}$$

$$H_1: \mu_{\text{best-GS010}} \neq \mu_{\text{best-Sham}}$$

Where  $\mu$  presents the mean change from baseline to Week 48 in LogMAR and “best” indicates best-seeing eyes.

The primary analysis will be performed on the ITT population. The change from baseline to Week 48 in the LogMAR acuity will be the primary response. The change from baseline of the best-GS010 eyes will be compared to the change from baseline of the best-Sham eyes (inter-subject comparison) using analysis of covariance (ANCOVA) including treatment as a main effect

- and baseline LogMAR

as a covariate in the model. The analysis will be performed based on alpha of 0.05. The statistical significance in favor of Best-GS010 eyes against Best-sham eyes will show evidence of the advantage of using GS010 in the best eye for halting visual acuity loss or improving visual acuity in subjects with LHON with a duration of vision loss of more than 6 months and up to 12 months. The difference in the mean change from baseline (adjusted mean difference) to Week 48 between the two treatment groups and associated 95% confidence interval will be reported.

The center will not be included in the analysis as the number of subjects recruited per site will be very small. However, stratification by geographical area will be performed as a sensitivity analysis. Neighboring regions will be pooled together to reach at least 9 subjects per geographical entity. The pooling will be performed during the masked review of data. An additional model will add the treatment by geographical area interaction to test for lack of generalizability of treatment effect.

The same analysis will be repeated for worst-GS010 eyes against worst-Sham eyes.

All the model diagnostics will be checked.

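### Protocol 12.4.1 opens better- and worse-eye comparisons only after an interaction pre-test at p<0.15, which selects exaggerated estimates; the SAP has dropped this gate, but the planned meta-analysis keeps a model switch with no stated criterion

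*Protocol*

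**What the plan says.** In Protocol 12.4.1 the primary analysis is the within-subject comparison of all GS010 eyes with all sham eyes. A second step fits "a model including the subject as a random factor, the treatment as a fixed factor as well as the eye status", together with the treatment-by-eye-status interaction. The trigger is "If the P-value of the interaction test is below 0.15 a potential interaction is detected". The consequence is "In that case the better-seeing eye treated with GS010 will be compared to the better-seeing eye treated with sham", and likewise for worse-seeing eyes, "in an ANCOVA model including the LogMAR at baseline and the treatment". The section gives these comparisons a power of 0.8 for about 30 letters but sets no significance level or multiplicity rule for them. Section 12.4.2 carries the primary approach over to Week 96.

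The SAP has no 0.15 threshold. In 9.5.1 the best-eye comparison is the primary analysis for FDA, where "The analysis will be performed based on alpha of 0.05". For EMA the best-eye comparison is secondary, and "Also for secondary analysis change of LogMAR from baseline in worst-seeing eyes treated with GS010 will be compared worst-seeing eyes treated with Sham". Neither is conditional on anything. Section 9.5.3 treats everything outside the primary analysis as supportive. The time-course model in 9.5.5 always contains the eye-status-by-treatment interaction and displays its p-value with no cut-off.

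The meta-analysis of RESCUE and REVERSE, also in Protocol 12.4.1, asks whether the treatment effect depends on time from onset. If the effect does not depend on eye status, the model has subject as a random factor and a treatment-by-onset-time interaction. Otherwise: "If the treatment effect is not the same in the better-and worse-seeing eye, a model will be fitted for the better-seeing eye", and another for the worse-seeing eye. These two models leave out the subject factor and list only baseline LogMAR, treatment and time from onset. No rule says how dependence on eye status is to be judged. The SAP text supplied does not specify the meta-analysis.

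**The concern.** Every subject has one GS010 eye and one sham eye, so the interaction is a between-subject contrast: the sum of both eyes' changes in subjects whose better eye was treated, minus the same sum in the other subjects. The better-eye and worse-eye comparisons are built from the same data. When chance makes the interaction large, it tends to make at least one of them large too. An eye-specific result that appears only because the gate opened has been selected for size, and its nominal p-value and confidence interval take no account of that. A gate with low power also makes a closed result weak support for reading the overall effect as applying to both eyes.

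The meta-analysis makes a similar switch. There it decides whether the pairing is used, and whether the question the meta-analysis exists to answer is in the model at all.

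**Working it through.** **Inputs.** 36 subjects and a between-eye correlation of 0 (Protocol 12.2, which adds that the correlation is usually positive, with no size given). An 18:18 split by which eye is treated (assumed from the minimization in Protocol 8.6). Interaction threshold 0.15 (Protocol 12.4.1). SD of the between-eye difference in change 0.594, and a difference of interest of 0.3 LogMAR (SAP 3.3). The opened tests are taken as two-sided at 0.05. That is an assumption, because Protocol 12.4.1 gives no level; it follows the SAP's best-eye analysis and the protocol's statement for the primary comparison that "The difference in the mean change from baseline to Week 48 between the two treatment groups and associated 95% confidence interval will be reported".

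**The plan's own figures.** n = ((1.960 + 1.036)/0.50)² = 35.9, so 36, as stated (normal approximation; the noncentral t gives 83.1% power at 36). For the SAP's second calculation, 0.3/0.594 = 0.505, and the noncentral t at n = 36 gives 83.8%, matching the stated 84%.

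**Correlation of gate and opened tests.** Let D_B and D_W be the treatment differences in better and worse eyes, each with variance v. Treatments are opposite within a subject, so corr(D_B, D_W) = −rho. The interaction is D_B − D_W, with variance 2v(1 + rho), and cov(D_B, D_B − D_W) = v(1 + rho). The correlation is (1 + rho)/sqrt(2(1 + rho)) = sqrt((1 + rho)/2): 0.71 at rho = 0, 0.87 at 0.5, 0.95 at 0.8.

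**Exaggeration under no effect (large sample).** The gate opens when |Z| > 1.44. The mean of |Z| given opening is 2 × 0.1415/0.15 = 1.89. The expected better-eye difference, in the direction of the observed interaction, is then 0.71 × 1.89 = 1.3 standard errors at rho = 0 and 0.87 × 1.89 = 1.6 at rho = 0.5. The true value is zero.

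**Error rates under no effect.** Simulated trials, 18 v 18, t-tests without baseline adjustment, 100,000 to 200,000 trials per rho:

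| | rho 0 | rho 0.5 | rho 0.8 |
|---|---|---|---|
| Better-eye test significant, given gate opens | 20% | 28% | 32% |
| At least one eye test significant, given gate opens | 39% | 50% | 50% |
| At least one significant, given gate stays shut | 4.7% | 1.9% | 0.4% |
| At least one significant and gate open (gated rule) | 5.7% | 7.3% | 7.6% |
| At least one significant, no gate | 9.6% | 8.9% | 7.9% |
| All-eyes primary or gated eye result | 10.0% | 11.6% | 11.9% |
| All-eyes primary or ungated eye result | 11.5% | 12.2% | 12.0% |

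The large-sample value of the second row peaks at 0.51, at rho = 0.7. If baseline predicts change (assumed correlation −0.3 to −0.5, between-eye baseline correlation 0.7) and only the opened ANCOVAs adjust for it, that row falls to 23 to 45% over rho 0 to 0.9.

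**Power of the gate for a 0.3 LogMAR interaction.** Single-eye SD s = 0.594/sqrt(2(1 − rho)); SE = sqrt(4s²(1 + rho)/18); critical t(34) = 1.47.

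- rho 0: s = 0.420, SE = 0.198, power 52%.
- rho 0.3: s = 0.502, SE = 0.270, power 37%.
- rho 0.5: s = 0.594, SE = 0.343, power 29%.
- rho 0.7: s = 0.767, SE = 0.471, power 23%.

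**The case against.** The strongest reply is that the SAP, which Protocol 12.1 makes the place for methodological detail, no longer uses the gate. For REVERSE itself the eye-specific comparisons will be run whatever the interaction shows. That stands, and it confines the REVERSE part of this point to unreconciled protocol text. It does not reach the meta-analysis, which the supplied SAP text leaves as the protocol wrote it.

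A reader might infer that the gate inflates the trial's error to 10 to 12%. The table does not support this. The excess over 5% comes from adding two unadjusted tests, and without the gate it is the same or slightly higher.

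A reader might also infer the classical two-stage crossover fault, in which a pre-test chooses the primary test. Nothing in 12.4.1 lets the interaction displace the all-eyes comparison; the gate only adds comparisons.

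A reader might take one half as the conditional rate. That needs a positive correlation of a size the documents do not give, and it lies near the maximum. It also counts results in both directions: given opening, at least one false result in favour of GS010 occurs in about 20 to 32% for rho 0 to 0.8.

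Finally, the meta-analysis paragraph does not mention 0.15, so carrying that threshold over is an inference. Its lack of any criterion is the defect. It is fair to add that a model with one eye per subject cannot estimate a subject effect, so dropping that factor follows from splitting the data. The criticism is of the split.

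**Conclusion.** The concern holds in a limited form. Given that the gate opens under no effect, at least one eye-specific test is nominally significant in about 40 to 50% of trials for rho from 0 to 0.8, and in fewer if baseline predicts change. Estimates reported only through the gate are selected and too large. A closed gate says little: power for a 0.3 LogMAR interaction is 52% at rho = 0 and 23 to 37% at rho 0.3 to 0.7. The gate does not raise the unconditional error.

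The practical consequences are two. Protocol 12.4.1 and SAP 9.5.1 disagree on whether the eye-specific comparisons are conditional, and the SAP gives one of them primary status. The meta-analysis switches models on an undefined criterion, and as written one branch omits the treatment-by-onset-time interaction it was set up to estimate.

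The figures rest on an 18:18 split, normal data, no missing values, opened tests at two-sided 0.05, and a between-eye correlation the documents do not supply.

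**What to change.** In Protocol 12.4.1, delete the p<0.15 trigger so that the text matches the SAP. State that better- and worse-eye estimates with 95% confidence intervals, and the interaction estimate with its interval, are always reported. They are supportive, except where the SAP names the best-eye test as primary.

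In the meta-analysis paragraph, replace the two branches with one paired model: subject as a random factor, treatment, eye status, time from onset, treatment-by-eye-status and treatment-by-onset-time, all kept whatever the interaction p-value. Repeat this specification in the SAP before the randomization code is broken, since Appendix V allows no SAP amendment after that.

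The change should not be presented as lowering the unconditional type I error, because it does not. The cost is wording and a slightly larger meta-analysis model, with no added subjects, visits or data.

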12.2 Sample Size

Sample size calculation is based on the primary endpoint (LogMAR) and on the paired comparison of treated and sham eye. There is no published data regarding the within subject variance and the sample size calculation through paired comparison will therefore be very speculative for two reasons. The first reason is the within subject correlation between right and left eye and the second reason is the absence of information on the within and between subject variance of the LogMAR. Usually the within subject correlation is positive and the use of a null correlation is conservative. The absence of information on the LogMAR requires a second rough approximation of the mean and variance of LogMAR because the mean of ETDRS (Lam et al. 2014) is highly correlated to the variance of ETDRS ($R^2 = 0.839$ for the log-log relationship). This correlation is in favor of the use of the LogMAR to stabilize the variance but the transformation from ETDRS mean and variance to LogMAR mean and variance requires additional assumptions. Starting with a mean 23.4 and a standard deviation of 28.3 (Lam et al. 2014) and a difference of 20 letters on average between treated and sham eye, using the relationship between the log mean and the log variance obtained with Lam et al. (2014) results (log variance = 1.743 log mean + 0.48, $R^2 = 0.839$) and assuming a perfect lognormal distribution of ETDRS, the difference in means of the lognormal distributions is 0.65 (3.32 - 2.67) and the pooled standard deviation of the log distributions is 0.914. Assuming no correlation between both eyes, the within subject standard deviation is $(2 \times 0.914^2)^{0.5} = 1.29$. The standardized difference in means is therefore $0.65/1.29 = 0.504$ rounded to 0.50. The sample size required to get a power of 85% is exactly 36 subjects.

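### A treatment-by-eye-status interaction p-value of 0.15 or more cannot verify that one pooled effect describes both better- and worse-seeing eyes: with 36 subjects, power for a 0.3 LogMAR difference is about 52% at best under non-negative between-eye correlation

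*Protocol*

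**What the plan says.** Protocol 12.4.1 states the premise for one overall effect: "The treatment effect reflects well the effect on the better- and worse-seeing eye if no marked interaction" exists between eye status and treatment. To verify it, the protocol fits a mixed model with subject, treatment, eye status and the treatment-by-eye-status term. The decision rule is "If the P-value of the interaction test is below 0.15 a potential interaction is detected". Only when that happens are better-seeing eyes compared with better-seeing eyes, and worse with worse. The protocol says those follow-on comparisons have 80% power for about 30 letters. It gives no power for the interaction test itself.

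The same section plans a RESCUE+REVERSE meta-analysis with two branches. The first begins "If the treatment effect does not depend upon the eye status, a model using the change from baseline as the response" and lists subject, treatment, time from onset and treatment by time from onset, without eye status. The second, used if the effects differ, fits a separate model for each eye type. The text names no test, margin or dataset for choosing between them.

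Whether the effect at Weeks 48 and 96 depends on the eye treated is a secondary objective (Protocol 2.2; SAP 2).

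The SAP has no 0.15 gate. In SAP 9.5.1, best-GS010 against best-sham is the FDA primary analysis, the worst-eye ANCOVA is always repeated, and both comparisons are EMA secondary analyses. The time-course model in SAP 9.5.5 contains an eye-status-by-treatment term, whose p-value goes on the graphs, and separate best-eye and worst-eye models are added.

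**The concern.** Failing to detect an interaction shows that effects are similar only if the test had a good chance of detecting a difference that matters. The protocol calls the step a verification but provides nothing to separate no difference from cannot tell. The trial was sized for the paired treated-versus-sham comparison, and the interaction does not share that precision.

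Two things depend on it. One is the answer to a stated objective, for which minimization on eye status was adopted. The other is the pooled LogMAR model, which would leave out the minimization factor when the effect is taken not to depend on it.

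**Working it through.** **Inputs**
- 36 subjects (Protocol 12.2; SAP 3.3).
- SD of the between-eye difference in LogMAR change at Week 48: 0.594 (SAP 3.3).
- 0.3 LogMAR, or 15 letters: the SAP's clinically reliable difference between treated and untreated eyes (SAP 3.3). Using it as the size of a difference between two treatment effects is my assumption.
- Threshold 0.15, taken as two-sided.
- 18 better-eye-treated and 18 worse-eye-treated subjects. Minimization aims at balance; the exact split is assumed.
- Between-eye correlation ρ of the changes. The documents plan with 0, say it is usually positive, and give no estimate. Values above 0 are assumptions.
- Equal variances in the two eyes, no missing data, and no baseline term (none is listed for this model).

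**The plan's own figures.** Protocol 12.2 gives "The standardized difference in means is therefore $0.65/1.29 = 0.504$ rounded to 0.50" and "The sample size required to get a power of 85% is exactly 36 subjects". The paired normal formula gives n = ((1.960 + 1.036)/0.50)² = 35.9, so 36. For the SAP's 84%, a paired t-test with n = 36 has SE = 0.594/√36 = 0.099; the noncentral t with 35 df gives 83.8%. Both reproduce.

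**What the interaction estimates.** Let B and W be the changes in the better and worse eye. Group 1 has the better eye treated, group 2 the worse eye.
- Effect in better eyes = mean(B, group 1) − mean(B, group 2).
- Effect in worse eyes = mean(W, group 2) − mean(W, group 1).
- Interaction = their difference = mean(B+W, group 1) − mean(B+W, group 2).

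This is a between-subject contrast of the sum of both eyes. With per-eye SD σ, SD(difference)² = 2σ²(1−ρ) and SD(sum)² = 2σ²(1+ρ). So SD(sum) = 0.594·√((1+ρ)/(1−ρ)), and SE = SD(sum)·√(1/18 + 1/18) = SD(sum)/3.

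**Results (noncentral t, 34 df, two-sided 0.15)**

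| ρ | SD(sum) | SE | Power for 0.3 | Missed | 95% CI half-width |
|---|---|---|---|---|---|
| 0 | 0.594 | 0.198 | 52% | 48% | 0.40 |
| 0.05 | 0.624 | 0.208 | 49% | 51% | 0.42 |
| 0.3 | 0.809 | 0.270 | 37% | 63% | 0.55 |
| 0.5 | 1.029 | 0.343 | 29% | 71% | 0.70 |
| 0.7 | 1.414 | 0.471 | 23% | 77% | 0.96 |

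Fitting the mixed model to simulated data gave 52.5%, 35.5% and 29.5% power at ρ = 0, 0.3 and 0.5. By normal approximation, 80% power would need 82, 152 or 246 subjects at those correlations.

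Zero correlation is conservative for the paired effect. With the SD of the difference fixed, it is the favourable end of the non-negative range for the interaction. A negative ρ would do better (65% at −0.2), but the protocol expects a positive one.

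**A larger difference.** Take 0 in better eyes and 0.6 in worse eyes. Power is 94%, 77% and 61% at ρ = 0, 0.3 and 0.5. In simulation, 5%, 17% and 30% of trials show a significant overall effect together with p≥0.15.

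**Pooled data.** With 72 subjects (36+36, 70 df, same SD), power for 0.3 is 75%, 55% and 42% at ρ = 0, 0.3 and 0.5.

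**The case against.** The strongest reply is that the SAP already deals with the main harm. Best-eye and worst-eye comparisons at Week 48 are run whatever the interaction shows, with adjusted differences and 95% CIs. The best-eye comparison is repeated at Week 96, and the time-course analyses add eye-specific models. A reader might infer that a drug doing nothing in better eyes could be reported as working in both. The documents do not support that: a null better-eye effect would be the FDA primary result. This stands, and it narrows the point.

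It does not remove it. Two eye-specific estimates are not an estimate of their difference with a CI. The time-course model offers a p-value, but it has no three-way term with visit, so that p-value is not specific to Week 48 or Week 96. The SAP text does not revise the protocol's branch for the pooled model.

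Other replies also have force:
- A reader might infer that the protocol treats p≥0.15 as proof of equal effects. It does not say so. It speaks of a potential interaction and of no marked interaction, and 0.15 is already lenient. What it does is offer no other check.
- A reader might infer that the test usually misses 0.3 LogMAR. At the planning correlation of 0 it misses 48%, just under half; the majority begins at about ρ = 0.05.
- Fixing 0.594 while raising ρ makes the per-eye SD rise from 0.42 to 0.77 at ρ = 0.7, which no document supports. If the per-eye SD is held at 0.42 instead, power is 45% at ρ = 0.3 and 42% at ρ = 0.5, still below 52%. That alternative departs from the SAP's observed SD of the difference.
- Linking the 0.15 rule to the meta-analysis branch is an inference. It is the only criterion stated for the LogMAR effect, but the branch does not cite it.
- The pooled LogMAR analysis asks mainly about time from onset, and the pooled responder model in Protocol 12.4.2 does include eye status.

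**Conclusion.** The point holds in limited form. The 0.15 threshold is the protocol's only check that the pooled effect represents both eye types, and the test behind it is weak: for a 0.3 LogMAR difference in effect, about 52% power at zero correlation and 37% or 29% at an assumed 0.3 or 0.5. A result of p≥0.15 should not be described as verifying equal effects.

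The consequence is confined to how the eye-dependence objective is answered and how the pooled LogMAR model is chosen. The main efficacy comparisons are unaffected.

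The figures rest on the 18+18 split, the SD of 0.594, equal eye variances, complete data and no baseline adjustment. A baseline covariate could raise power somewhat. The correlation is unknown, so the range matters more than any single value.

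**What to change.** 1. In Protocol 12.4.1, remove the 0.15 gate so that the eye-specific comparisons are unconditional, as in the SAP.
2. In the protocol and SAP, report the treatment-by-eye-status interaction (better-eye effect minus worse-eye effect) with its 95% CI at Week 48 and at Week 96. Do not describe p≥0.15 as showing no dependence.
3. In the pooled RESCUE+REVERSE LogMAR model, delete the conditional branch and always include eye status and treatment by eye status.

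An equivalence rule requiring the CI to lie within ±0.3 LogMAR should not be adopted. The SAP's 0.3 is a treated-versus-untreated difference, not a margin for an interaction. With 36 subjects and a true interaction of zero, simulation meets the rule about 0.1% of the time at ρ = 0 and never at 0.3 or above, so its answer is fixed in advance.

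The cost is wording, one interval at each of two visits, and two degrees of freedom in the pooled model. The interval will be wide, with a half-width of about 0.40 LogMAR or more at 36 subjects if the correlation is not negative. The report will probably have to say that dependence on eye status is not excluded.

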12.4.2 Secondary Analysis

The treatment estimate at Week 96 will be based on the same statistical approach as the primary endpoint analysis. Another analysis will compare time course of the response up to Week 96 using the mixed model procedure. The responder analyses at both Week 48 and Week 96 will be based on a McNemar test for paired samples. To verify whether the treatment effect is dependent upon the better-seeing eye or the worse-seeing eye at study entry, a test of homogeneity of subgroups (better-seeing or worse-seeing eye treated) effects in stratified paired binary data ([Zhao 2014](#)) will be performed.

Like the primary endpoint, a meta-analysis will be performed combining both studies (GS-LHON-CLIN-03A (RESCUE) and study GS-LHON-CLIN-03B (REVERSE)). A conditional logistic model will be used to assess the effect of better- and worse-seeing eye at study entry and the effect of time from onset of disease and the effect of treatment.

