### 4.3 PREDETERMINED COVARIATES AND PROGNOSTIC FACTORS

RGC layer, INL, ONL thickness/volume and topographical maps of these anatomical regions, best or worst-seeing eye (eye status) as determined prior to randomization and duration of vision loss at the time of treatment could be significant prognostic factors for the treatment effect. Sensitivity analysis will be performed for RGC layer thickness/volume and topographical map and eye status (best or worst-seeing eye) and duration of vision loss at the time of treatment by including them in the primary model as a covariate.

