### Sensitivity Analyses

The primary analysis with the same model will be repeated for the following lists.

- 1) Per protocol
- 2) Randomized subjects even if they were not treated and assigned treatment by randomization instead of actual treatment received
- 3) Secondary handling of missing data
- 4) Model with geographical area effect
- 5) Model excluding major outliers if any
- 6) Analysis of absolute Week 48 LogMAR values
- 7) Baseline GCL thickness/volume and topographical map
- 8) Best or worst-seeing eye (eye status) added as a binary covariate
- 9) Duration of vision loss at the time of treatment added as a covariate in the model

All these analyses will be presented in a forest plot displaying treatment effect, 95% confidence intervals and p-value. The analysis will also be presented in tabular format.

- 10) Non-parametric Analysis: Wilcoxon signed-rank test will be performed as a sensitivity analysis to compare between all-GS010 eyes and all-Sham eyes

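### The pooled RESCUE and REVERSE analysis is meant to test whether the treatment effect depends on time from onset, but its eye-specific and responder models list no treatment-by-onset term.

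*Protocol*

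**What the plan says.** Protocol 12.4.1 gives the meta-analysis a specific task: to "verify whether the treatment effect at Week 48 as well as at Week 96 is dependent upon the time from onset of disease". Two models follow.

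- **No dependence on eye status.** The response is the change from baseline, with subject random, treatment fixed and time from onset as a covariate. In addition, "the interaction between the treatment and the time from the onset will be fitted".
- **Dependence on eye status.** "If the treatment effect is not the same in the better-and worse-seeing eye", one model is fitted to better-seeing eyes and another to worse-seeing eyes. The subject factor is dropped and "the LogMAR at baseline, the treatment, and the time from onset of disease will be included". No interaction is named, and no threshold is given for choosing this branch. The only threshold nearby belongs to the REVERSE analysis in the same section: "If the P-value of the interaction test is below 0.15 a potential interaction is detected".

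Protocol 12.4.2 adds a responder meta-analysis and likens it to the one for the primary endpoint: "A conditional logistic model will be used to assess the effect of better- and worse-seeing eye at study entry and the effect of time". The time meant there is that since onset, and treatment is listed as a third effect. Again no interaction is named.

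The readable SAP does not specify the meta-analysis. SAP 5.4 defines duration of vision loss from an onset date for each eye.

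**The concern.** Whether a treatment effect depends on time from onset is a question of effect modification. It needs a term that lets the effect vary with onset. The first model has that term; the eye-specific models and the responder model, as listed, do not.

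Protocol 12.1 says that improvement from gene transfer may be greatest early in the disease, and this meta-analysis is where the protocol proposes to examine that. If eye status matters, the continuous-endpoint analysis returns an average effect in each eye stratum, with no estimate or test of how it changes with duration. Protocol Appendix V rules out SAP amendments after the code is broken and treats later additions as post hoc, so an interaction added then would not count as prespecified.

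**Working it through.** **1. What the eye-specific model can identify.** The listed terms give, with B baseline LogMAR, T treatment (0/1) and x time from onset:

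E[change] = a + b·B + t·T + g·x

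The treatment effect is t at every x. Suppose the true effect is t + d·x, with x centred. With 1:1 allocation the fitted treatment coefficient is the average effect t, and the fitted onset coefficient is g + d/2, a mixture of prognosis and half the interaction. Neither isolates d.

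A simulation illustrates this. It used 72 subjects (36 + 36, from the enrolment goals in SAP 3.3), a mean effect of -0.30 LogMAR, a per-eye SD of 0.42, onset uniform over 0-180 and 181-365 days (the first range is an assumption), and g set to -d/2:

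| Change in effect across 0-365 days (d) | Additive model: treatment | Additive model: onset | Onset test rejects | Interaction test rejects when the term is added |
|---|---|---|---|---|
| 0 | -0.302 | 0.000 | 5.6% | 5.3% |
| 0.3 | -0.300 | 0.002 | 4.5% | 13.1% |
| 0.6 | -0.300 | 0.005 | 5.0% | 38.9% |
| 0.9 | -0.301 | -0.001 | 4.3% | 71.9% |

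The additive fit looks the same in every row. The value of g was chosen to make the point; another g would move the onset coefficient but would still not separate g from d.

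**2. What the responder model can identify.** Take the subject as the matched set. Among subjects with one responding eye, the log-odds that it is the GS010 eye is

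t + g·(x_GS010 - x_sham) + h·(difference in eye status)

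- If onset is one value per subject, x_GS010 - x_sham = 0 and g drops out. The within-pair design for treatment and onset has rank 1 of 2. With treatment and treatment-by-onset it has rank 2, so the interaction is estimable.
- If onset is per eye, g is estimable, but it is a main effect of having been affected longer, not a change in the GS010 effect.

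**3. How often the eye-specific branch is used.** If the P < 0.15 rule decides, a valid test selects the branch 15% of the time when there is no true eye-status difference, and more often when there is one.

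**4. What the added term would deliver.** The documents give no power for the meta-analysis. The SD comes from SAP 3.3: 0.594 for the between-eye difference in change. The 84% power stated there for 0.3 LogMAR with 36 subjects reproduces (83.8%, paired t).

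Per-eye SD = 0.594/√(2(1 - r)), where r is the between-eye correlation:
- r = 0: 0.594/√2 = 0.42
- r = 0.5: 0.594/√1 = 0.594

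Assume onset is even over 0.5 to 12 months, so its SD is 11.5/√12 = 3.32 months. The interaction slope then has approximate SE = 2·SD/(√72 × 3.32):
- SD 0.42: 0.84/28.2 = 0.030 LogMAR per month
- SD 0.594: 1.188/28.2 = 0.042 LogMAR per month

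A fall of 0.3 LogMAR over 12 months is a slope of 0.025 per month, or 0.84 SE and 0.59 SE respectively. Simulated power at two-sided 0.05:

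| Fall in effect over 12 months | SD 0.42 (r = 0) | SD 0.594 (r = 0.5) |
|---|---|---|
| 0.3 LogMAR | about 12% | about 9% |
| 0.6 LogMAR | about 36% | about 21% |
| 0.9 LogMAR | about 67% | about 40% |

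**The case against.** The best defence is that the list of terms is not expressly exhaustive. The sentence can be read as stating changes from the preceding model, in a paragraph whose purpose is effect dependence, so the missing interaction may be a drafting ellipsis. This is plausible. But the first model names its interaction and this one does not, so a programmer working from the text would leave it out, and the readable SAP does not put it back. A separate meta-analysis plan may exist; it is not among these documents.

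On responders, the effect-modification aim is written for the primary endpoint and reaches 12.4.2 only through the comparison with it. That section speaks of the effect of time from onset. A reader might infer that the responder model yields nothing on duration. That holds only if onset is one value per subject, which the documents do not say.

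A reader might also extend the fault to the SAP. SAP 4.3 says duration and other factors "could be significant prognostic factors for the treatment effect", and the EMA sensitivity list has "Duration of vision loss at the time of treatment added as a covariate in the model"; the FDA list has a matching item. These are checks that the primary estimate survives covariate adjustment and do not claim to test effect modification. An interaction there would also yield little: about 6%, 8% and 14% power with 36 better-seeing eyes, onset 6 to 12 months, SD 0.42 and the same slopes.

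Finally, this is a branch of a supportive analysis, and SAP 9.5.3 spends all the alpha on the primary endpoint. That stands, and it limits the weight of the point.

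**Conclusion.** The point holds for the eye-specific models in Protocol 12.4.1: as written, they cannot answer the question the meta-analysis is set. It holds in weaker form for the responder model in 12.4.2. There the onset term either cancels (one onset per subject) or estimates a main effect (onset per eye), and in neither case shows effect modification. The 15% figure depends on borrowing the P < 0.15 rule.

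This is worth correcting, but it does not threaten the trial. The REVERSE primary test, its alpha and its 36 subjects are untouched.

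Three further inferences are not supported:

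- **That the two trials were split by duration in order to answer this.** RESCUE's entry window is not in these documents; the 0.5-month lower limit above is an assumption.
- **That the added term would be well powered.** A smaller per-eye SD such as 0.30 would need a between-eye correlation of 1 - 0.594²/(2 × 0.30²) = -0.96, whereas Protocol 12.2 expects the correlation usually to be positive. That points to an SD of 0.42 or more.
- **That a single onset date misplaces the second eye by a third of the range.** The median two-month delay is a third of REVERSE's six-month window, but the model pools both trials. Over the assumed range it is 2/11.5, about a sixth.

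**What to change.** - **Protocol 12.4.1:** add the treatment-by-time-from-onset interaction to both the better-eye and the worse-eye model. Report its slope with a 95% CI, labelled supportive.
- **Protocol 12.4.2:** add the treatment-by-onset interaction to the conditional logistic model.
- **Both:** state that each eye's own onset date is used, as SAP 5.4 already does.

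The cost is a change of wording and one model term in each place, with no new data. The downside is an imprecise estimate, so a non-significant interaction should not be read as evidence that duration does not matter. The edit should be made before the randomization code is broken. SAP 4.3 and the duration items in the EMA and FDA sensitivity lists need no change on this account.
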